8.0 Study Withdrawal/Discontinuation

Reasons for Withdrawal

A study subject will be discontinued from participation in the study if any of the following occur: (1) Unacceptable AE; (2) Development of any exclusion criteria; and (3) Subject withdrawals consent to continue in the research for any reason. The development of an inter-current illness, or other medical condition or situation would not risk the continued participation in the study since the injection occurs once, after the patient has been entirely screened based upon the inclusion and exclusion criteria.

Handling of Withdrawals

Subjects who withdraw from the study will still be followed-up since they are receiving the same therapeutic modality whether they were enrolled in the trial or not. Safety data on any subject discontinued because of an AE or SAE will be collected and reported to the investigators, who will then communicate it to their corresponding IRBs. If voluntary withdrawal occurs, the subject should be asked to continue scheduled evaluations, complete an end-of-study evaluation, and be given appropriate care under medical supervision until the symptoms of any AE resolve or the subject's condition becomes stable.

Termination of Study

The study will be terminated if: (1) the patients target number has been achieved and a complete follow-up has been accomplished; or (2) similar SAE patterns occur (5 consistent events in patients receiving the same therapy). In the first case, statistical analysis will be performed, whereas in the second, recruitment will be halted and AEs/SAEs reported to all investigators, IRBs, and if unexpected and deemed associated with the drug injected, to the FDA (via the IRB).

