3.0 Inclusion/Exclusion Criteria

The center enrolling patients (UTMB) will obtain approval through its own institution review board (IRB). The study will be posted on clinicaltrials.gov. The subjects in this study will be recruited from the investigators' private clinics. Prior to enrollment, the investigator will obtain informed written consent from the subjects. All of the investigators are CITI trained. They will review the consent form with patients and allow sufficient time for potential subjects to read the consent form and consider the risks and benefits of participation. Investigators will leave the clinic room to allow patients to consult with friends and family. If patients decide to defer the decision to enroll, they will be allowed to return at a later date. It will be emphasized to patients that they need not participate in the study to receive a subacromial injection. If they choose not to participate, they will be offered a subacromial injection that consists of the medication that is mutually agreed upon between their physician and them. No coercion to participate in the study will take place.

Adults at least 18 years of age seen in clinic with a diagnosis of severe or recalcitrant shoulder impingement syndrome and to whom the investigator has offered a subacromial injection will be invited to participate.

Subjects meeting any of the exclusion criteria at baseline will be excluded from study participation. Exclusion criteria are: allergy/intolerance to steroids or NSAIDs symptoms less than one month, pregnancy or breastfeeding, pre-existing asthma, uncontrolled psychiatric illness, previous shoulder injection within the past three months, evidence of other confounding shoulder pathology on plain radiographs such as calcific tendonitis, MRI evidence or history of a full-thickness rotator cuff tear, active comorbidities of the ipsilateral extremity such as cervical radiculopathy, moderate to severe glenohumeral arthritis, systemic inflammatory conditions, kidney or liver disease, gastrointestinal (GI) ulcers, bleeding disorders, pending litigation or work-related claims related to the shoulder, previous shoulder surgery on the affected shoulder, evidence of local infection, evidence of adhesive capsulitis, and evidence of shoulder instability.

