7.0 Adverse Events or Unanticipated Problems involving Risk to Participants or Others

Most of these contra-indications are retrieved from the medications package inserts. Due to the randomization and blinding design of the study, a contra-indication to either drug (methylprednisolone acetate or ketorolac tromethamine) is considered an absolute contra-indication for the patient to be enrolled in the study. Subjects meeting any of these conditions at baseline will be excluded from study participation. These conditions include: allergy/intolerance to steroids or NSAIDs symptoms less than one month, pregnancy or breastfeeding, pre-existing asthma, psychiatric illness, previous shoulder injection within the past three months, evidence of other confounding shoulder pathology on plain radiographs such as calcific tendonitis, MRI evidence or history of rotator cuff tear, active comorbidities of the ipsilateral extremity such as lateral epicondylitis and cervical radiculopathy, moderate to severe glenohumeral arthritis, systemic inflammatory conditions, kidney or liver disease, gastrointestinal (GI) ulcers, bleeding disorders, pending litigation or work-related claims related to the shoulder, previous shoulder surgery on the

affected shoulder, evidence of local infection, evidence of adhesive capsulitis, evidence of shoulder instability, and bilateral shoulder pain.

The International Council for Harmonisation of Technical Requirements for Pharmaceuticals for Human Use (ICH) defines an adverse event (AE) as any untoward medical occurrence in a patient or clinical investigation subject administered a pharmaceutical product regardless of its causal relationship to the study treatment. An AE can therefore be any unfavorable and unintended sign, symptom, or disease temporally associated with the use of medicinal product. The occurrence of an AE may come to the attention of study personnel during study visits and interviews of a study recipient presenting for medical care, or upon review by a study monitor.

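### Section 8.0 gives conflicting rules for a patient who develops an exclusion criterion, and the plan does not say whether ASES is collected or analysed after a non-voluntary discontinuation

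*Combined protocol and SAP*

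**What the plan says.** Section 8.0 (Reasons for Withdrawal) gives three grounds for discontinuing a subject. The first two read "1) Unacceptable AE; (2) Development of any exclusion criteria"; the third is withdrawal of consent. The next sentence reads "The development of an inter-current illness, or other medical condition or situation would not risk the continued participation in the study", and its reason is that the injection is given only once, after full screening.

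Section 8.0 (Handling of Withdrawals) makes three statements about data:
- In general: "Subjects who withdraw from the study will still be followed-up".
- After an adverse event: "Safety data on any subject discontinued because of an AE or SAE will be collected and reported to the investigators".
- After voluntary withdrawal: "If voluntary withdrawal occurs, the subject should be asked to continue scheduled evaluations".

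The exclusion criteria appear twice. Section 3.0 introduces them with "Subjects meeting any of the exclusion criteria at baseline will be excluded from study participation", and section 7.0 also applies its list at baseline. The lists differ: section 3.0 has "MRI evidence or history of a full-thickness rotator cuff tear", section 7.0 has "MRI evidence or history of rotator cuff tear".

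Section 9.0 makes week-12 ASES the main outcome of a non-inferiority comparison and plans 20 patients per arm. It adjusts for baseline ASES only if the arms differ at baseline. It defines no analysis population, no method for missing scores and no rule for scores obtained after discontinuation.

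**The concern.** Two investigators who both follow section 8.0 could treat the same patient differently: one discontinues, the other keeps the patient in. What happens next to the week-12 score is also open, both in collection and in analysis.

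This matters because the loss need not be random. Under Risks, section 6.0 names infection and tendon rupture as local effects of the steroid, and GI ulceration, renal failure and bleeding as effects of ketorolac. Each has a counterpart among the exclusion criteria: local infection, rotator cuff tear, GI ulcers, kidney disease, bleeding disorders. The second ground for discontinuation could therefore remove patients for reasons tied to the assigned drug. If the missing patients do worse than the rest and the loss falls mainly on ketorolac, the observed deficit shrinks and a false non-inferiority claim becomes more likely. If it falls mainly on steroid, the bias runs against non-inferiority.

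**Working it through.** **1. The plan's own figures.** Section 9.0: 4 × (1.64 + 0.84)² × 12.3² / 12² = 4 × 6.1504 × 151.29 / 144 = 25.85, so 26 in total; 26 / 0.8 = 32.5, so 33; 40 planned. These reproduce and are not disputed. With 20% loss, 40 × 0.8 = 32 remain (power about 86.7%). If a further 10%, 15% or 20% of the 40 were discontinued and left out, 28, 26 or 24 would remain (power about 82.5%, 80.0%, 77.2%). The plan tolerates (40 − 26) / 40 = 35% non-evaluable, so the issue is bias more than sample size.

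**2. The two sentences, side by side.**

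| Event after injection | Discontinuation list | Next sentence |
|---|---|---|
| Listed condition (e.g. local infection, GI ulcer, adhesive capsulitis, cuff tear) | Discontinued | Participation unaffected |
| Unlisted condition | Silent, unless an unacceptable AE | Participation unaffected |

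The conflict is confined to the first row.

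**3. Which list.** Section 7.0 adds lateral epicondylitis and bilateral shoulder pain, and omits the qualifiers full-thickness (cuff tear) and uncontrolled (psychiatric illness). New pain in the other shoulder, or a partial tear, would meet one list and not the other.

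**4. What is collected afterwards.**

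| Reason | General follow-up | Scheduled evaluations | Safety data |
|---|---|---|---|
| Voluntary withdrawal | Yes | Requested | Until any AE resolves or the patient is stable |
| Unacceptable AE | Arguably yes | Not stated | Named |
| New exclusion criterion | Arguably yes | Not stated | Not stated, unless also an AE |

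**5. Effect of leaving patients out.** If a fraction p of an arm is left out and its mean lies D points below that of the others, the arm mean rises by p × D.
- One of 20 with D = 20: (1/20) × 20 = 1 point.
- The ketorolac-minus-steroid difference shifts by p_K × D_K − p_S × D_S. Equal rates alone do not make this zero. With an assumed 10% lost in each arm, D_K = 30 and D_S = 10, the shift is 3 − 1 = 2 points, so a true difference of −12 looks like −10. With 20 per arm and SD 12.3, simulation puts the false non-inferiority rate at about 12% instead of 5%.

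**6. Generic outcome-related dropout, for scale only.** From section 9.0: 20 per arm, SD 12.3, steroid mean 68.7, alpha 0.05 (one-sided, as z = 1.64 implies). Assumed: the formula's 12 points as margin, true week-12 difference −12, the same SD and steroid mean at week 4, correlation 0.5 or 0.7 between weeks 4 and 12, and the week-12 score lost when week-4 ASES is below 40, 45 or 50. Unadjusted pooled t, lower one-sided 95% limit against −12, 100,000 trials per case. With all scores kept the error is 5%.

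| Week-4 ketorolac deficit | Mean number lost, ketorolac / steroid (cut-off 40; 45; 50) | Error, r = 0.5 | Error, r = 0.7 |
|---|---|---|---|
| 12 | 1.75/0.20; 3.42/0.54; 5.86/1.29 | 7.7, 9.8, 12.6% | 9.2, 13.0, 18.2% |
| 6 | 0.65/0.20; 1.50/0.54; 3.03/1.29 | 5.8, 6.5, 7.5% | 6.2, 7.5, 9.2% |
| 0 | 0.20; 0.54; 1.29 in each arm | 4.9–5.0% | 4.9–5.0% |

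**The case against.** **Follow-up is already promised.** All three grounds stand under Reasons for Withdrawal, so the general sentence under Handling of Withdrawals can be read as covering all of them, and the safety-data sentence as adding a duty rather than limiting one. This stands in part. A reader might infer that ASES stops after a non-voluntary discontinuation; the documents do not say that. But the general sentence names neither ASES nor the visits, so they do not secure the week-12 score either.

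**The second sentence may mean only unlisted conditions.** On that reading nothing conflicts. But its wording has no such limit, and its reason, a single injection already given, applies equally to listed conditions.

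**The simulation does not model the rule.** This stands. No passage makes a low ASES score a ground for discontinuation, and the top case loses 5.86 of 20 (29%) on ketorolac, which nothing in the documents supports. It would be wrong to read 8–18% as this trial's error rate. Only the 1-point arithmetic describes the defect itself.

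**Further injection or surgery.** Because both lists include a recent shoulder injection and previous shoulder surgery, a reader might infer that either event during follow-up triggers discontinuation. The documents do not say so: the lists apply at baseline, and section 6.0 says that no additional injections will be needed. No figure here rests on that reading.

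**Covariate adjustment is a separate topic.** Largely fair: it does not recover lost scores. It is in the fix because the same analysis paragraph has to be completed.

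**Conclusion.** The point holds as a contradiction plus an omission. Section 8.0 conflicts with itself for listed conditions that arise after injection, the two exclusion lists differ, ASES is not named after non-voluntary discontinuation, and section 9.0 has no rule for those scores. None of this depends on the simulation.

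A reader might go further and conclude that the rule favours ketorolac. The documents do not support that: arm-specific harms are named on both sides and no rates are given, so direction and size are unknown. Nor would equal discontinuation rates settle the matter, since the outcomes of those discontinued also count. For generic dropout under the stated assumptions, the false non-inferiority rate is about 8–18%, 6–9% or 5% for a week-4 ketorolac deficit of 12, 6 or 0 points. That range shows sensitivity and is not an estimate for this trial. The change should be made; confidence is medium, because how often the rule would be used is unknown.

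**What to change.** 1. The sponsor should reconcile the two sentences in section 8.0 and state which exclusion list, section 3.0 or section 7.0, is meant. Which clinical rule is right is not for this review to say.
2. State that ASES at weeks 2, 4 and 12 continues to be collected after any discontinuation, unless consent for data collection is withdrawn.
3. In section 9.0, analyse all randomised patients in the assigned arm, using scores collected after discontinuation. Include baseline ASES and sex (the randomisation stratum in section 4.0) as covariates whether or not baseline scores differ.
4. Name in advance the method for week-12 scores that are still missing, for example a repeated-measures model using weeks 2 and 4, and show completers as a sensitivity analysis. Such a model relies on the observed scores to account for the loss, and how much it would repair was not tested here, so item 2 is the main safeguard.

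Cost: protocol and analysis wording and slightly more analysis work. The questionnaire is already scheduled and takes about four minutes according to section 6.0. The figures 26, 33 and 40 do not change.

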9.0 Statistical Considerations

This study is a non-inferiority multicenter randomized controlled double-blinded trial that evaluates the efficacy of injectable methylprednisolone acetate monotherapy and ketorolac monotherapy in the treatment of patients with subacromial impingement syndrome in the outpatient setting. Therapeutic arms consist of two groups (groups 1 and 2 receiving injectable methylprednisolone acetate and ketorolac, respectively). Patients will be evaluated and compared based on the ASES self-assessment score (ranging between 0 and

100). Our main outcome is ASES score at the 12-week time-point, with details of analysis provided in the next paragraph. We will also, as exploratory analysis, compare the functional outcome at 2 and 4 weeks post-injection. We will report summary statistics containing means and standard deviations of ASES scores for each treatment arm at each time point. We will determine whether there is non-inferiority of ketorolac at each time point.

Based on historical data (at 12 weeks post injection), the mean ASES score in the control (steroid) group is expected to be about 68.7, and the standard deviation about 12.3 [18]. The ASES patient self-assessment is a validated questionnaire that can quantify pain and decreased function of the affected shoulder, and it is usually filled out by patients as part of routine care for shoulder pain [19, 20]. Based on a review of the literature, the minimum clinically relevant effect size was determined to be ranged between 12 and 17 [21]. We therefore chose to use the lower value as reference. We calculated the minimum sample size (n) that would be required in order to ensure that the study has an 80% power with an enrollment ratio of 1, using the following formula:

$$2n = \frac{4(z_{1-\alpha} + z_{1-\beta})^2 \sigma^2}{\Delta^2} = \frac{4(1.64 + 0.84)^2 \cdot 12.3^2}{12^2} = 25.8 \approx 26$$

In this formula, Δ represents the absolute difference between the means (μ) of groups 1 and 2 ($\Delta=|\mu_2 - \mu_1|$); σ , the variance of the mean; n, the sample size per arm; α , the probability of type 1 error (0.05); β , the probability of type II error (0.2); and z, the critical z value for a given α or β . To this end, 13 individuals per arm (26 in total) should have been enrolled and completed the trial. Assuming that 20% of patients will be lost to follow-up [3], we will attempt to enroll $26/0.8 = 33$ patients. For this end, we would aim at including a total of 40 patients in the study, which correspond to 20 patients per therapeutic arm. We will also assess whether there are differences in baseline scores between the 2 groups. In the case that the ASES scores differ, we will control for baseline value for each patient by including it as a covariate in a linear regression analysis, with covariates being baseline value and treatment group.

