2.0 Rationale and Specific Aims

Because of the current conflicting evidence, the lack of long-term follow-up, and the multiple potential benefits to the society, we aim to compare subacromial ketorolac versus steroid for the treatment of shoulder impingement. We hypothesize that patients with external shoulder impingement who are treated with a subacromial injection of 80 mg methylprednisolone in 1% lidocaine versus 60 mg ketorolac in 1% lidocaine have similar outcomes based on the American Shoulder and Elbow Surgeon (ASES) self-assessment score (ranging between 0 and 100) at 2, 4, and 12 weeks post-injection. If the follow-up could not be performed exactly at 2, 4, or 12 weeks post-injection, investigators will allow examination and measurements at ± 3 days. The study will be performed in The University of Texas Medical Branch (UTMB, coordinating center). This will help us determine the efficiency of either therapeutic modality in the management of patients with subacromial impingement syndrome.

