4.0 Treatment Assignment/Randomization

The following measures will be taken to ensure double-blinded randomization. Prior to the initiation of the study, computer-generated tables will be created in Excel to assign each patient a randomization number. This master list will be kept with a statistician and research coordinators, who do not have any patient contact. Based on his/her corresponding generated number (even or odd), the patient will be assigned to his/her therapeutic arm (methylprednisolone and ketorolac, respectively). The statistician will use an equally weighted random number generator to create these assignments. Therefore subjects will have an equal chance of being assigned to either treatment arm. Separate lists for male and female participants will also be generated to ensure equal gender participation. The statistician will then prepare an opaque envelope for each subject number. The unique subject number will be written on the visible outside surface of each envelope. The corresponding treatment arm assignment will be inside the envelope. The statistician will seal each envelope individually and send all of the envelopes to the research coordinator ([name]) prior to patient enrollment. The sealed opaque envelopes will be divided equally among the clinics and kept in locked containers in the research coordinator's office. The study staff will not have access to the envelopes. After ensuring that the patient has completed the ASES questionnaire (to establish a baseline prior to the injection), the study staff will contact [name] or [name] to provide them with the patient's first and last names as well as the MRN. The research coordinator will open one of the sequentially numbered envelopes to assign each patient the corresponding subject number (written on the outside of the envelope), and a member of the clinic staff will prepare the appropriate injection (see below) for the assigned treatment arm. The syringe will be covered with opaque tape prior to being given to the surgeon for administration. The injection will take place in a private clinic room in compliance with the Health Insurance Portability and Accountability Act (HIPAA) guidelines. The blinded surgeon will administer the injection into the subacromial space using standard bony landmarks from the posterolateral approach. The clinic staff will file the drug accountability log after preparing the injection and they will not disclose the treatment arm assignment to the patient nor the provider. This will maintain the blinding for both the patient and research surgeons. Patients' subject number will be recorded on their consent form and in their electronic medical record. Envelopes will be destroyed at the end of the study by the research coordinators. The statistician will unlock the master list only after patient enrollment and follow-up are complete, or if mandated by any regulatory body. Blinding will also be uncovered in case of a patient developing an adverse event while being followed in the trial.

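### Section 9 leaves the week-12 non-inferiority margin and pass rule implied rather than written, and lets observed baseline scores decide whether the only named model is used

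*Combined protocol and SAP*

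**What the plan says.** Section 9.0 opens with the design: "This study is a non-inferiority multicenter randomized controlled double-blinded trial". It then fixes the endpoint and promises the method: "Our main outcome is ASES score at the 12-week time-point, with details of analysis provided in the next paragraph". It also says that non-inferiority of ketorolac will be determined at each time point, with weeks 2 and 4 exploratory.

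What follows is mainly the sample-size calculation. A clinically relevant effect of 12 to 17 points is taken from the literature, and of that range the plan says: "We therefore chose to use the lower value as reference". The formula uses 1.64, 0.84, an SD of 12.3 and 12. The key to the formula states that Δ "represents the absolute difference between the means" of groups 1 and 2, and labels σ a variance, although 12.3 was introduced as the standard deviation.

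The only analysis text comes at the end of the section: "We will also assess whether there are differences in baseline scores between the 2 groups", and then "In the case that the ASES scores differ, we will control for baseline value for each patient", by linear regression on baseline value and treatment group. Apart from that, the plan offers means and standard deviations by arm. Section 4.0 already has every patient complete the ASES questionnaire "to establish a baseline prior to the injection".

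**The concern.** Three things that a non-inferiority analysis needs are unwritten or left open.

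- **Margin.** Δ is defined as a difference between means, which is how a superiority alternative is described. The 12 is a reference value, with no statement that it is the largest acceptable deficit and no assumed true difference.
- **Pass rule.** No interval, confidence level or success criterion for week 12 is stated. A reader has to infer them from the 1.64 in the formula.
- **Model.** The observed baseline comparison decides whether the named model is used. There is no criterion for differ and no analysis for the other case. Under Section 4.0 the master list is unlocked only after follow-up is complete (adverse-event unblinding and regulatory demands aside). So baseline scores would ordinarily be compared by arm when the week-12 results are also to hand.

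At stake is whether the primary verdict is fixed in advance, and whether the trial uses the precision that its baseline data offer.

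**Working it through.** **Inputs from Section 9.0.** SD 12.3; value used for Δ 12; α = 0.05 with z = 1.64; power 80% with z = 0.84; 1:1 allocation; 20% loss; 40 enrolled. Completers are therefore 40 × 0.8 = 32, or 16 per arm.

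**Assumptions not in the documents.** Correlation r between baseline and week-12 ASES of 0.3, 0.5 or 0.7; differ taken to mean baseline p < 0.05; an unadjusted t comparison otherwise.

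**1. The plan's figure.** 2n = 4 × (1.64 + 0.84)² × 12.3² / 12² = 25.85, rounded to 26. Then 26 / 0.8 = 32.5, so 33. Both reproduce.

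**2. What the figure can mean.** The non-inferiority formula puts (margin - true deficit)² in the denominator. With margin 12 and true deficit 0 this is again 12². A one-sided superiority calculation with true difference 12 gives the same 13 per arm. The arithmetic is right for the declared design, but it does not show which quantity Δ was meant to be.

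**3. Power and the implied pass rule, unadjusted.** SE = 12.3 × √(2/n). The largest observed ketorolac deficit that still passes is 12 - t(0.95, 2n - 2) × SE. Power is from the noncentral t at true difference 0.

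| Completers per arm | SE | Cut-off | Power |
|---|---|---|---|
| 13 | 4.824 | 12 - 1.711 × 4.824 = 3.75 | 78.0% |
| 16 | 4.349 | 12 - 1.697 × 4.349 = 4.62 | 85.3% |
| 20 | 3.890 | 12 - 1.686 × 3.890 = 5.44 | 91.7% |

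The unwritten confidence level matters. With a two-sided 95% interval at 16 per arm the half-width is 8.88, and the cut-off falls from 4.62 to 12 - 8.88 = 3.12.

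**4. Effect of adjusting, 16 per arm.** SE is multiplied by √(1 - r²), giving 4.148, 3.766 or 3.106. With balanced baselines the cut-off is 12 - 1.699 × SE = 4.95, 5.60 or 6.72.

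**5. The plan's rule against always adjusting.** Simulated with bivariate normal scores, equal variances, 16 per arm, and a pass if the lower 90% limit exceeds -12.

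| | r = 0.3 | r = 0.5 | r = 0.7 |
|---|---|---|---|
| Power at true difference 0, plan's rule | 85% | 86% | 87% |
| Power at true difference 0, always adjusted | 87% | 92% | 98% |
| Different verdicts, true difference 0 | 5% | 8.5% | 12% |
| Different verdicts, true deficit 6 | 8.5% | 15.5% | 27% |
| False passes at true deficit 12, plan's rule | 4.8% | 4.5% | 4.0% |

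**6. Dependence on chance imbalance, true deficit 12.** In about 14% of trials baseline favours ketorolac by more than 1 SE without reaching p < 0.05, so the plan's rule would not adjust. The unadjusted false-pass rate there is about 10, 13 or 17% for the three correlations. In the mirror case, with baseline favouring steroid by as much, it is about 1.7, 0.5 or below 0.1%. The adjusted analysis stays near 5% in both.

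**The case against.** The strongest reply is that the intended rule can be reconstructed. Section 9.0 names the design, the tested arm, the endpoint and the time point; 12 is the only candidate threshold, and 1.64 with α = 0.05 fixes a one-sided test. For an unadjusted analysis the rule follows: the lower one-sided 95% limit must lie above -12. That stands. A reader might infer that no conclusion could be drawn from the plan, but the documents do not support that. The rule is implied but not written, and the model is not fixed.

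Three other inferences are tempting and also fail.

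- **That the definition of Δ makes the sample size wrong.** It does not; 26 completers suit margin 12 with true difference 0.
- **That choosing the model on baseline scores inflates false passes or favours ketorolac.** On average it does neither. The raised rate in one direction of imbalance is offset by a lowered rate in the other.
- **That Section 2.0, which hypothesises that the arms "have similar outcomes based on the American Shoulder and Elbow Surgeon (ASES) self-assessment score" at three time points, sets a competing primary objective.** Section 9.0 settles this by making week 12 the main outcome and the earlier weeks exploratory.

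It is also fair to say that the trigger uses baseline scores and not outcomes, that even the conditional rule exceeds the planned 80% at 16 per arm, and that the size of the loss depends on a correlation and a trigger that the documents do not give. None of this supplies the missing trigger, the analysis for the other case, or a reason to forgo a covariate already collected.

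**Conclusion.** The concern holds as a gap in pre-specification. The margin and pass rule are implied by the sample-size formula and never stated, and the primary model depends on an undefined look at the data. The sample size and the average type I error are sound: 26 completers give about 80% power by the plan's formula (78% with t).

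At 16 completers per arm with SD 12.3, the conditional rule gives up roughly 2, 6 or 11 points of power at true difference 0. Its verdict would differ from the always-adjusted one in 5 to 12% of trials there, and in 8.5 to 27% at a true deficit of 6. These are disagreement rates, not error rates. All rest on correlations of 0.3 to 0.7 and a p < 0.05 trigger, both assumed. The textual gap does not depend on them.

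**What to change.** Amend Section 9.0 before the master list is unlocked:

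1. Make the week-12 analysis always the linear regression on treatment and baseline ASES, whatever the baseline comparison shows.
2. Define Δ as the non-inferiority margin, using the sponsor's own 12 points, with the reason for that choice stated and an assumed true difference of 0. Label σ the standard deviation.
3. State that ketorolac is non-inferior only if the lower limit of the two-sided 90% interval (one-sided 0.05) for ketorolac minus steroid from that model is above -12.

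With the margin kept at 12, the sample size does not change. No new data are needed. The cost is one degree of freedom for the covariate and wording in Section 9.0. One consequence should be accepted openly: an observed deficit beyond the cut-off must be reported as non-inferiority not shown, even when the arms do not differ significantly.
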